### **7.3 Assessment and Verification of Compliance**

All doses of the study vaccine should be administered in the clinical unit under direct observation of clinic personnel and recorded in the eCRF. Clinic personnel will confirm that the participant has received the entire dose.

The location (right or left arm, or other location if required), if the full dose was administered, date, and timing of all doses of study vaccine will be recorded in the participants' eCRF. If a participant is not administered study vaccine, the reason for the missed dose will be recorded.

### **7.4 Prior and Concomitant Therapies**

Administration of medications, therapies, or vaccines will be recorded in the eCRF. Concomitant medications will include all medications (including vaccines) taken by the participant from the time of signing the ICF through 182 days after the first vaccination (or through the early termination visit if prior to that time). Prescription and over-the-counter (OTC) drugs will be included. Do not record herbals, vitamins, and supplements.

Concomitant medications will be collected through Day 70 for all unsolicited AEs, and through EoS for all MAAEs, SAEs, or AESIs (including PIMMCs). Receipt of any approved or deployed COVID-19 or influenza vaccine should also be recorded through EoS. Sites will record the date(s) and brand of the approved or deployed COVID-19 vaccine received.

#### **7.4.1 Prohibited Therapies**

Subjects may receive all concomitant medications and procedures deemed necessary to provide adequate health care during the study, with the exception of those specified in the exclusion criteria and as indicated below. Routine medical standards of care are permitted, including vaccines needed for emergent indications (eg, tetanus booster in response to a penetrating injury).

The following therapies are prohibited within the specified timeframes of study conduct:

- No routine (non-emergent) vaccines will be allowed until after study Day 70 (ie, 14 days after the second dose of test vaccine).
- No influenza vaccine will be allowed within 2 months prior to first study vaccination until after the last study visit (Day 182).
- No investigational product (drug/biologic/device) within 90 days prior to first study vaccination until after the last study visit (Day 182).
- No chronic administration (defined as more than 14 continuous days) of any immunosuppressant medication within 3 months of first study vaccination until the last study visit (except topical, inhaled, or intranasal steroids or short-term oral steroids with course lasting  $\leq$  14 days). Topical tacrolimus and ocular cyclosporine are permitted.

## 8 SAFETY MONITORING

The timing and frequency of all safety assessments are listed in the SOE ([Table 1](#)). Solicited and unsolicited AEs will be graded for severity using the provided criteria ([Appendix 2](#)). Recording of solicited and unsolicited AEs will be conducted by electronic data capture (EDC). AESIs, including PIMMCs, will also be monitored (see [Appendix 1](#) for details).

### 8.1 Definitions

- **AE** – An AE is any untoward medical occurrence associated with the use of an intervention in humans whether or not it is considered intervention-related. Any abnormal laboratory test results or other safety assessments (eg, physical exam, vital signs measurements), including those that worsen from baseline, considered clinically significant in the medical and scientific judgement of the investigator (ie, not related to progression of underlying disease) will be considered AEs.
- **SAE** – An event is considered “serious” if, in the view of either the Investigator or Sponsor, it results in any of the following outcomes:
  - Death
  - A life-threatening AE (An event is considered “life-threatening” if, in the view of either the Investigator or Sponsor, its occurrence places the patient or subject at immediate risk of death. It does not include an AE or suspected adverse reaction (AR) that, had it occurred in a more severe form, might have caused death.)
  - Inpatient hospitalization or prolongation of existing hospitalization. In general, hospitalization signifies that the participant has been detained, usually involving an overnight stay, at the hospital or emergency ward for observation and/or treatment that would not have been appropriate in the physician’s office or outpatient setting. Hospitalization for elective treatment of a pre-existing condition that did not worsen from baseline is not considered an SAE.
  - A persistent or significant incapacity or substantial disruption of the ability to conduct normal life functions
  - A congenital anomaly/birth defect
  - Important medical events that may not result in death, be life-threatening, or require hospitalization may be considered serious when, based upon appropriate medical judgment, they may jeopardize the patient or subject and may require medical or surgical intervention to prevent one of the outcomes listed in this definition. Examples of such medical events include allergic bronchospasm requiring intensive treatment in an emergency room or at home, blood dyscrasias or convulsions that do not result in inpatient hospitalization, or the development of drug dependency or drug abuse.
- **Causality or relatedness** – For each AE/SAE, the investigator must document in the medical notes that they have reviewed the AE/SAE and have provided an assessment of causality as follows.
  - Not Related: There is no reasonable possibility of relationship to study vaccine. The AE does not follow a reasonable temporal sequence from administration of study

vaccine or can be reasonably explained by the participant's clinical state or other factors (eg, concurrent diseases, and concomitant medications).

- Related: There is a reasonable possibility of relationship to study vaccine. The AE follows a reasonable temporal sequence from administration of study vaccine and cannot be reasonably explained by the participant's clinical state or other factors (eg, concurrent diseases, or concomitant medications), represents a known reaction to study vaccine or other vaccines in its class, is consistent with the known pharmacological properties of the study vaccine, and/or resolves with discontinuation of the study vaccine (and/or recurs with re-challenge, if applicable).
- **Adverse reaction** – An AR is any AE caused by a drug.
- **Suspected adverse reaction (SAR)** – An SAR is any AE for which there is a reasonable possibility that the drug caused the AE. For the purposes of IND safety reporting, “reasonable possibility” means there is evidence to suggest a causal relationship between the drug and the AE. SAR implies a lesser degree of certainty about causality than AR.
- **Unexpected** – An event is considered unexpected if it is not listed in the IB, is not listed at the specificity or severity that has been observed, or, if an IB is not required or available, is not consistent with the risk information described in the General Investigational Plan or elsewhere in the IND. Unexpected also refers to events that are mentioned in the IB as occurring with a class of drugs or as anticipated from the pharmacological properties of the drug but are not specifically mentioned as occurring with the particular drug under investigation.
- **Severity or intensity** – The severity (or intensity) of an AE/SAE refers to the extent to which it affects the participant's daily activities and will be classified as mild, moderate, or severe using the following criteria:
  - Mild: These events require minimal or no treatment and do not interfere with the participant's daily activities.
  - Moderate: These events result in a low level of inconvenience or require minor therapeutic measures. Moderate events may cause some interference with normal functioning.
  - Severe: These events interrupt a participant's usual daily activity and may require systemic drug therapy or other treatment. Severe events are usually incapacitating.

If the severity of an AE/SAE changes, the most intense severity should be reported. An AE/SAE characterized as intermittent does not require documentation of the onset and duration of each episode.

## 8.2 Documenting Adverse Events

At every study visit, participants will be asked a standard question to elicit any medically related changes in their well-being. They will also be asked if they have been hospitalized, had any accidents, used any new medications, or changed concomitant medication regimens (both prescription and OTC medications).

In addition to participant observations, AEs will be documented from any data collected on the AE page of the eCRF or other documents that are relevant to participant safety.

Care will be taken not to introduce bias when detecting AEs, MAAEs, AESIs (including PIMMCs) and SAEs. Open ended and non-leading verbal questioning of the participant is the preferred method to enquire about AE occurrences. AESIs (including PIMMCs) will be inquired about according to the specific diseases listed in [Appendix 1](#).

When an AE/AESI/SAE occurs, it is the responsibility of the investigator to review all available documentation (eg, hospital progress notes, laboratory reports, and diagnostics reports) related to the event. The investigator will then record all relevant AE/SAE information in the eCRF.

It is not acceptable for the investigator to send photocopies of the participant's medical records in lieu of completion of the AE/SAE eCRF page. There may be instances when copies of medical records for certain cases are requested. In this case, all participant identifiers, with the exception of the participant number, will be redacted on the copies of the medical records before submission. The investigator will attempt to establish a diagnosis of the event based on signs, symptoms, and/or other clinical information. Whenever possible, the diagnosis (not the individual signs/symptoms) will be documented as the AE/SAE.

The following variables will be recorded for each AE: verbatim/AE description and date for AE start and stop, severity, seriousness, causality, whether the AE caused the participant to not receive the second dose of study vaccine, any other action taken, and the outcome. A new AE must be recorded if the severity of the AE changes.

Should an SAE have an outcome of death, the report should contain a comment regarding the co involvement of progression of disease, if appropriate, and should assign main and contributory causes of death.

#### 8.2.1.1 Assessment of Causality

There may be situations in which an SAE has occurred and the investigator has minimal information to include in the initial report. However, it is very important that the investigator always make an assessment of causality for every event before the initial transmission of the SAE data. The investigator may change their opinion of causality in light of follow-up information and send a SAE follow-up report with the updated causality assessment. The causality assessment is one of the criteria used when determining regulatory reporting requirements.

The investigator should consider the following, before reaching a decision on causality assessment:

- Time relationship between study vaccine injection and event's onset.
- Re-challenge following second vaccination, if applicable.
- Medical history.
- Study treatment.
- Mechanism of action of study vaccine.
- Class effect.
- Concomitant treatments in use.
- Withdrawal of study treatment.
- Lack of efficacy/worsening of existing condition.
- Possible vaccine enhancement of COVID-19.

- Erroneous treatment with study medication or concomitant medication.
- Protocol-related process.

#### 8.2.1.2 Action Taken with Study Vaccine Due to AE

The action taken with study vaccine should be recorded using one of the following:

- No action taken.
- Next dose delayed.
- Permanently discontinued/withdrawn from further study vaccination (with date).
- Not applicable.

#### 8.2.1.3 Other Action Taken

Details of any other actions taken should be specified:

- Specific therapy/medication.
- Surgical or medical procedure.
- Prolonged hospitalization.

#### 8.2.1.4 AE Outcome

Each AE should be rated according to one of the following outcomes:

- Recovered/resolved.
- Recovering/resolving.
- Not recovered/not resolved.
- Recovered with sequelae/resolved with sequelae.
- Fatal.
- Unknown.

### 8.2.2 Time Frame for Collection

All AEs reported or observed during the study will be recorded on the AE page of the eCRF.

Medical occurrences that begin prior to the first dose of study vaccine will be recorded on the Medical History/Current Medical Conditions section of the eCRF not the AE section.

All unsolicited AEs of any severity will be collected from the time of first study vaccination through Day 70 (ie, until 14 days after the second vaccination). Any relevant observations made prior to the first dose of study vaccine are to be recorded on the AE eCRF but will not be considered TEAEs and will be reported separately from TEAEs.

MAAEs and AESIs (including PIMMCs) will be collected from the time of first study vaccination until EoS.

All SAEs will be collected from signing of informed consent until completion of the EoS.

Participants who receive an approved/authorized vaccine (see Section 7.2.4.1), will be encouraged to remain in the study for safety follow-up and safety assessments will be performed via the timelines and mechanisms as described herein. In addition, all vaccine administration errors, AEs, SAEs, cases of multisystem inflammatory syndrome, and hospitalized or fatal cases

of COVID-19 following vaccination with the approved/authorized must be reported following local regulatory reporting guidance for safety events that occur in subjects who receive approved/authorized vaccines within the study.

At any time after completion of the EoS visit, if an investigator learns of an SAE that could reasonably be considered related to study vaccine, they should promptly notify the Sponsor.

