**Table 1 Schedule of Events for Study 2019nCoV-ICC-E-101**

	Study Day:	0	7	28	56	63	70	84	182 
	Window (days):	0	+ 3	+ 3	+ 5	+ 3	+ 5	± 7	± 14
	Study Visit:	1	2	3	4	5	6	7	8
Informed consent	X								
Medical history	X								
Inclusion/exclusion criteria, including determination of baseline seropositivity to SARS-CoV-2 based on SARS-CoV-2 vaccination documentation or history of prior SARS-CoV-2 infection	X								
Randomization	X								
Demographics	X								
Prior/concomitant medications	X	X	X	X	X	X	X	X 	X 
Vital signs measurements	X 	X	X	X 	X	X	X	X	X
Urine pregnancy test	X			X			X 		
Physical examination (at baseline and as required thereafter) 	X	X	X	X	X	X	X	X	X
Vaccination	X 			X 			X 		
Reactogenicity / Participant Diary Completion	X 	X		X 	X				
Blood sampling for SARS-CoV-2 (anti-NP) antibodies	X 					X		X	
Blood sampling for SARS-CoV-2 immunogenicity (ELISA), HAI serology, and influenza virus MN 50 assay (testing performed at Novavax)	X 		X	X 		X	X	X	
Blood sampling for SARS-CoV-2 MN 50 assay	X		X	X		X	X	X	
Whole blood sampling and PBMC harvest for SARS-CoV-2 spike-specific T cell counts at a pre-specified subset of sites 	X	X			X			X	
Unsolicited AEs	X	X	X	X	X	X			
MAAEs	X	X	X	X	X	X	X	X	X
SAE	X	X	X	X	X	X	X	X	X
AESIs (including PIMMCs)	X	X	X	X	X	X	X	X	X

ELISA = enzyme-linked immunosorbent assay; EoS = End of Study; HAI = hemagglutination inhibition; IFN $\gamma$  = interferon gamma; IL-2 = interleukin-2; MAAE = medically attended adverse events; MN = microneutralization; NP = nucleoprotein; PBMC = peripheral blood mononuclear cells; PCR = polymerase chain reaction; PIMMC = potential immune-mediated medical conditions; SAE = serious adverse event; SARS-CoV-2 = severe acute respiratory syndrome coronavirus 2; Th1 = Type 1 T helper; Th2 = Type 2 T helper; TNF $\alpha$  = tumor necrosis factor alpha.

1. Vital signs to be captured pre-vaccination and between 30 to 60 minutes post-vaccination.

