2. Participants should be free of acute illness (defined as the presence of a moderate or severe illness in the clinical judgment of the investigator) with or without fever, or an oral temperature  $\geq 38^\circ\text{C}$  in order to receive the test article injection. Participants presenting with an acute illness on screening/Day 0 may return to the trial site within the next 7 days to receive their injection provided symptoms have resolved.
3. Starting on the first vaccination day (Day 0) and for 6 days thereafter (Day 0 through Day 6, inclusive), participants will maintain diaries for daily recording of their body temperature and any AE spontaneously offered (reactogenicity).
4. Starting on the second vaccination day (Day 56) and for 6 days thereafter (Day 56 through Day 62, inclusive), participants will maintain diaries for daily recording of their body temperature and any AE spontaneously offered (reactogenicity).
5. Participants presenting with an acute illness on Day 56 may return to the trial site within the next 7 days to receive their second vaccination. If a participant has experienced any AEs/AESIs/SAEs between trial Days 0 and 56, the Day 56 vaccination may be administered or delayed for up to 7 days based on the investigator's discretion.
6. Day 0 prior to vaccination.
7. Including IL-2, TNF $\alpha$ , CD40L, and IFN $\gamma$ .
8. EoS.
9. After physical examination at baseline determines eligibility, subsequent physical examination assessments are symptom directed as triggered by AE or symptom reports.
10. In order to receive a complete 2-dose series of COVID-19 vaccine, participants from treatment group O will receive a third dose of vaccine consisting of 5  $\mu\text{g}$  SARS-CoV-2 rS nanoparticle vaccine and 50  $\mu\text{g}$  Matrix-M1 at Day 70. Note that because Vaccine Group O is the only treatment group receiving a vaccine at Day 70, Vaccine Group O participants and site staff will

be unblinded to participant's treatment status from Day 70 onwards. The Sponsor recognizes this partial unblinding and assesses it as having minor impact to the data.

11. After Day 70, only those concomitant medications taken for any of the following events will be recorded: any MAAEs, SAEs, or AESIs (including PIMMCs).
12. Participants in Vaccine Group O who are women of childbearing potential will have a urine pregnancy test performed at the Day 70 visit prior to dosing.

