#### 7.1.2.2 Dosing and Administration

The SARS-CoV-2 rS antigen will be mixed with Matrix-M1 adjuvant in the clinic pharmacy, or an area designated for this function, according to the Pharmacy Manual on the day of administration by a qualified member of study site personnel. The vaccine should be administered according to standard aseptic practice by qualified study site personnel in a way so as to maintain the blind, as directed in the Pharmacy Manual.

Following in-clinic mixing according to the Pharmacy Manual, the SARS-CoV-2 rS with Matrix-M1 vaccine can be stored at room temperature, in a secured location, for up to 3 hours in the mixing vial or 1 hour in the final administration syringe. DO NOT FREEZE or REFRIGERATE once mixed.

The SARS-CoV-2 rS with Matrix-M1 adjuvant vaccine regimen will comprise 2 identical IM injections (Day 0 and Day 56 for Group P; and Day 56 and Day 70 for Group O) ([Table 3](#); [Table 4](#)).

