### 9.3.6.2 Unsolicited Adverse Events

Unsolicited AEs will be coded by SOC and PT using MedDRA terms. Unsolicited AEs will be summarized overall and by the vaccine group and by SOC/PT, as well as by severity and relationship to the study vaccine to present the number and percentage with its corresponding exact 95% CIs using Clopper-Pearson method. For multiple occurrences of an AE in the same participant, a participant will be counted only once, using the most severe or most related occurrence for the summarization by severity or relationship to the study vaccine, respectively. Unsolicited AEs will be summarized through Day 70.

All MAAEs, AESIs (predefined list), and SAEs, throughout the study will be collected from the first vaccination through Day 182 after first vaccination and summarized overall and by the study vaccine group as well as by severity.

A listing of participants with unsolicited AEs, MAAEs, AESIs, and SAEs will also be produced from the first vaccination through Day 182.

The denominator is based on the Safety Analysis Set. Missing data will not be imputed while handling of partial dates will be described in the SAP.

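### Scheduled collection of ordinary unsolicited AEs ends at Day 70, when Group O alone receives a third injection, and no SAP safety period starts at that injection

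*Protocol*

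**What the plan says.** **The dose.** Protocol Table 1, footnote 10, says "participants from treatment group O will receive a third dose of vaccine" at Day 70. Section 6.1.2.2 gives that visit a +5-day window. Section 7.1.2.2 places the two rS injections at "Day 56 and Day 70 for Group O", so the Day 70 dose is part of that group's regimen.

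**The collection limit.** Section 8.2.2: "All unsolicited AEs of any severity will be collected from the time of first study vaccination through Day 70". The only explanation given, there and in SAP 7.1.2, is that Day 70 is 14 days after the second vaccination. In Table 1 the "Unsolicited AEs" row is marked at Days 0, 7, 28, 56, 63 and 70 and not later. For AEs, the Day 84 and Day 182 visits (6.1.2.3, 6.1.3.1) list MAAEs, SAEs and AESIs only. Section 6 limits the diary to Days 0–6 and 56–62.

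**What follows dose 3.** Section 6.1.2.2 keeps participants in clinic for at least 30 minutes, with severe reactions noted as AEs that day. Section 8.7 requires vital signs before and after injection on vaccination days. MAAEs, SAEs and AESIs run to Day 182.

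**The SAP.** Section 6.1 counts Group O's Day 70 exposure. Section 7.1.1 ties solicited AEs to the Day 0 and Day 56 doses. Section 7.1.2 uses Days 0–70, 71–182 and 0–182, all counted from Day 0, and allows other periods without naming any.

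**Broader wording.** Section 8.2.2 opens with "All AEs reported or observed during the study will be recorded on the AE page of the eCRF". Section 8.2 says "At every study visit, participants will be asked a standard question to elicit any medically related changes in their well-being". Section 8.2.3.4 speaks of diary use after each vaccination but names only Days 6 and 62. Section 9.3.6.2 says "A listing of participants with unsolicited AEs, MAAEs, AESIs, and SAEs will also be produced from the first vaccination through Day 182".

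**The concern.** The primary objective is to describe the safety and tolerability of the regimens in the study, and Group O's regimen has three injections. The collection limit was set around dose 2 and applied unchanged to a group dosed again at the visit where collection stops.

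What is at stake is a mild or moderate AE after dose 3 that is neither medically attended nor an AESI. No scheduled step asks for it after the injection day, and no table would show it as following that dose. A low count for Group O after Day 70 could then be read as good tolerability when it partly reflects that nobody was asked. The dose also has its own setting: it is the only one planned about two weeks after a previous adjuvanted injection.

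**Working it through.** **1. The plan's own figure.** With dose 2 on Day 56, follow-up to Day 70 is 70 − 56 = 14 days, as stated. With dose 2 on Day 61, the end of its +5 window, it is 70 − 61 = 9 days. Table 1, footnote 5, lets dose 2 be delayed up to 7 days, to Day 63, which gives 70 − 63 = 7 days.

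**2. The same count after dose 3.** With Day 70 read as a study day:
- Injection on Day 70: 70 − 70 + 1 = 1 calendar day, the injection day.
- Injection on Days 71–75: 0 days.

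If Day 70 means the visit, the AE assessment at that visit is still the last one scheduled, so nothing is scheduled after the injection day on either reading.

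**3. Interval between doses 2 and 3**, counting visits from Day 0:
- Protocol windows: 70 − 61 = 9 to 75 − 56 = 19 days.
- With the footnote 5 delay: 70 − 63 = 7 days at the least.
- With the ±4 window printed in SAP 1.1 (dose 2 on Days 52–60): 70 − 60 = 10 to 75 − 52 = 23 days.
- If the Day 70 visit were instead counted 14 (+5) days from the actual dose 2: 14 to 19 days.

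Doses 1 and 2 are 56–61 days apart, or up to 63 with the delay.

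**4. Share of injections.** Planned injections of 5 µg rS with 50 µg Matrix-M1 are 2 × 40 = 80 (Group P), 40 (Group O, Day 56) and 40 (Group O, Day 70), 160 in all. A diary and scheduled unsolicited-AE collection follow 80 + 40 = 120. The other 40 / 160 = 25% have neither after the injection day.

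**5. When a later visit could pick events up.** The Day 84 visit (±7, Days 77–91) comes 77 − 75 = 2 to 91 − 70 = 21 days after dose 3. On the SAP appendix window (+5, Days 84–89) it comes 84 − 75 = 9 to 89 − 70 = 19 days after. The Day 182 visit (±14, Days 168–196) comes 168 − 75 = 93 to 196 − 70 = 126 days after.

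**6. Detection.** Protocol 9.2.1 states an 87% chance of seeing at least one AE of 5% incidence among 40 participants: 1 − 0.95^40 = 87.1%, so the figure reproduces. It presumes that such AEs are collected. Suppose only a share m of them reaches the database because they qualify as MAAEs, SAEs or AESIs. The documents give no m, so this is an assumption. The chance is 1 − (1 − 0.05m)^40: 0% at m = 0, 18.2% at 0.10, 39.5% at 0.25 and 63.7% at 0.50.

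**7. Placement in the SAP tables.** A same-day event after a Day 70 injection falls in Days 0–70, together with events after doses 1 and 2. For an injection on Day 75, the Days 71–182 period includes 75 − 71 = 4 whole days before the injection.

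**The case against.** **It looks deliberate.** The objective limits solicited AEs to the first two doses and unsolicited AEs to 70 days. SAP 7.1.1 names Group O when it restricts the overall solicited summary to the two initial doses. The third dose is given so that the group completes two COVID-19 doses. This stands as far as the stated endpoints go, and it is the main reason the point is minor. The documents acknowledge the unblinding that this dose causes, but not the gap in AE collection.

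**A reader might infer that the protocol contradicts itself about recording after Day 70.** The documents do not support so strong a claim. Protocol 9.3.1 lists unsolicited AEs through 70 days separately from the classes followed to Day 182, and Section 7.4 collects concomitant medications for unsolicited AEs through Day 70. The opening of 8.2.2 can be read as saying which eCRF page to use. The visit question in 8.2 also serves to elicit MAAEs, SAEs and AESIs. The Day 182 listing covers several classes, and SAP 7.1.2 words it as unsolicited AEs including those classes. What remains is loose wording to tidy.

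**Safety after dose 3 is covered, and the formulation is well known.** The first part is partly true: observation, vital signs, symptom-directed examinations and three AE classes remain. On the second, Protocol 2.1.5.2 describes the same formulation given 21 days apart in trials that enrolled 4,164 + 244 = 4,408, then 15,139 and 29,868 people. That lowers the stakes, but those were not third injections following qNIV with 75 µg Matrix-M1.

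**The events can be separated anyway.** Dose dates and AE dates are recorded, and the SAP permits other periods. This holds for whatever was recorded. It does not recover events that were never elicited.

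**Conclusion.** The point holds as a minor one. Beyond the injection day, ordinary AEs after Group O's third injection have no scheduled collection, and none at all if the injection is given on Days 71–75. No SAP period is tied to that injection. Up to 40 participants in one of 16 groups are affected.

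Two stronger inferences should be resisted. Safety follow-up after dose 3 is not absent, since MAAEs, SAEs and AESIs run to Day 182 and have their own Days 71–182 summary. The primary endpoints are not compromised either: they, the between-group solicited comparisons in SAP 7.1.1 and the DoE modelling do not use AEs of this kind after dose 3.

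The figures assume that all 40 planned participants receive dose 3, that visits are counted from Day 0, and that the printed windows are followed apart from the footnote 5 delay.

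**What to change.** **If Group O's third dosing is still open:** extend unsolicited-AE collection for that group to 14 days after the actual third-injection date, the same nominal span as after dose 2. Use the existing Day 84 visit, and add a telephone contact only where that visit falls earlier than 14 days.

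**In SAP 7.1.2, in either case:** present Group O events with onset on or after the third-injection date separately from the Days 0–70 table. Among the variables for each AE, Protocol 8.2 lists "verbatim/AE description and date for AE start and stop" but no time of day, so flag same-day events as of uncertain order.

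**If dosing is complete:** apply only the SAP separation, and state in the report that ordinary AEs after dose 3 were not systematically collected. This may well be the situation, since this protocol version is dated 06 May 2022 and the synopsis projected a stop in March 2022.

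**Wording, if the protocol is amended:** make clear how the visit question in 8.2, the first sentence of 8.2.2, the diary sentence in 8.2.3.4 and the Day 182 listing in 9.3.6.2 relate to the Day 70 limit.

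**Cost:** a short amendment and AE questions for 40 participants at a planned visit, with some calls; or SAP and report text alone. The added data would come from unblinded participants with no concurrent control, so they would be descriptive only.
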